## 9. Informed consent procedures

At each site it is the responsibility of the Principal Investigator or appropriately trained delegate, i.e. research nurse, to obtain consent from each subject prior to participation in this trial. All staff taking consent will be trained in taking consent and this will be evidenced on the on the delegation log. They will also have appropriate Good Clinical Practice (GCP) training.

The consent process will take place face to face or via a locally approved remote method (phone, video conferencing etc.). All potential participants will be provided with a copy of the latest versions of the patient information sheet and informed consent form together with an explanation of the aims, methods, anticipated benefits and potential hazards of the trial. This will be done either in person (preferred), via email or by post. The patients will be given the opportunity to ask questions about the study to a medically qualified member of the research team (i.e., doctor). All patients will be given a minimum of 24 hours between the time they are approached about the study and the time when consent is given. Prior to consent a member of the research team will confirm how consent will be provided by the patient (face to face, email or post) and this will be documented on the informed consent form itself. For those patients who have not been contacted face-to-face, the signed consent form will be returned via email or by post and counter-signed a member of the research team.

For patients who are consented to participate in the trial a copy of the patient information sheet and signed informed consent form will be filed in the medical notes. Patients who are consented but not entered into this study should be recorded

OSIRIS Protocol v2.0 20.11.2023 Page **15** of **46** 

(including reason not entered) on the screening log in the Investigator Site File. Original signed consent forms will be kept by the investigators and a copy will be given to the participant. The discussion and the consenting process will be documented in the patients' medical records. If any further safety information arises, which may result in significant changes in the risk/benefit analysis, the patient information sheet and informed consent form must be reviewed and if applicable updated accordingly.

The Principal Investigator has overall responsibility for the informed consent of participants at their site and will ensure that any person delegated responsibility to participate in the informed consent process is duly authorised, trained, and competent to participate according to the ethically approved protocol, principles of Good Clinical Practice (GCP), and Declaration of Helsinki. If delegation of consent occurs, then details will be provided in the site delegation log.

The right of a participant to refuse participation without giving reasons will be respected. The participant will remain free to withdraw at any time from the study without giving reasons and without prejudicing their further treatment and will be provided with a contact point where they may obtain further information about the study. Where a participant is required to re-consent (for example if new Research Safety Information becomes available during the study, or following an amendment that affects the participant, or new information needs to be provided to a participant) it is the responsibility of the Principal Investigator to ensure this is done in a timely manner and prior to the next use of the investigational device (where applicable).

## 10. Writing, reading and translation considerations

If verbal translation is needed, this will be done via a hospital interpreter as per usual practice.

## 11. Eligibility criteria

#### 11.1 Hospital inclusion criteria

 Provide services for high-risk patients in one or more of the following surgical procedures: elective colorectal bowel resection for cancer, hip-replacement, or abdominal aortic aneurysm surgery

OSIRIS Protocol v2.0 20.11.2023 Page **16** of **46** 

#### 11.2 Patient inclusion criteria

- Patients contemplating elective colorectal bowel resection for cancer, hipreplacement, or abdominal aortic aneurysm surgery
- Age 60 years and over
- Age-adjusted Charlson co-morbidity index ≥3

## 11.3 Patient exclusion criteria

- Inability or refusal to provide informed consent
- Patients expected to die within 12 months of treatment\*
- \* Determined by the treating clinician which may include consultant surgeons and anaesthetists leading the patient care.

# 12. Study procedures

12.1 Schedule of measurements for each visit

Visit	Pre-surgical /surgical clinic	Index decision making episode	Post-surgical clinic visit	Surgery	Hospital discharge	30-day follow-up after surgery ± 3 days	180-day follow-up after index decision ± 3 days
Data sources	In person and/or medical records	In person	In person or via telephone	Medical records	Medical records	Medical records and telephone interview	Medical records and telephone interview
Eligibility	×						
Informed consent	×	X¹					
Demographics	х						
NHS number, gender, date of birth, postcode	Х						
Co-morbidities	X						
EQ-5D-5L	×		Х			Х	Х
SF-12	×						Х
Decision aid		Х					
Details of planned and actual treatment		Х		Х			
SDM-Q9			$X^2$				
Health services resource use questionnaire			Х				Х
Complications						X 	
Patient vital status					Х	X 	Х
Patient discharge location					Х	X 	
Decision Regret Score							х
Follow-up interview		X 	X 			X 	х

<sup>1 If obtained before the surgical clinic, consent should be confirmed before the intervention takes place  Patient identifiable data collected for NHS Digital  Within 48h of decision making

<sup>4Where possible and appropriate
The interview can be completed either immediately after the consultation or subsequently over the phone
 Data collected from 30 days after surgery (only applicable if a patient has had surgery)

#### 12.2 Randomisation method

Clusters (hospitals) will be randomised to either intervention or control with a 1:1 allocation ratio. Random permuted blocks randomisation with block sizes of m=4 and 2 will be used. This is a restricted randomisation scheme without stratification. A manual randomisation system (see 12.3) will be used and no adaptive element is envisaged.

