## 12.3 Randomisation procedure

The code creating the randomisation list will be prepared by the trial statistician. The live allocation list will be generated by an independent statistician from within the Pragmatic Clinical Trials Unit (PCTU). Manual randomisation will be carried out remotely by the PCTU. A member of the research team who is un-blinded will be authorised to request randomisation of a cluster via email to the named independent statistician who will return the allocation also via email within one working day. PCTU will designate a standby who can provide allocations should the independent statistician be unavailable. Further details will be explained the Data Management plan which will be agreed and signed off between the trial study team and PCTU.

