## 21. Compliance

The Chief Investigator will ensure that the protocol and study is conducted in compliance with the principles outlined in the Medical Device Regulations 2002 and subsequent amendments, current UK Policy Framework for Social and health care research (2017), ISO14155 GCP guidelines, the World Medical Association Declaration of Helsinki, the Sponsor's and study specific SOPs, and other regulatory requirements. The study will not commence until approval from the relevant competent authorities, ethics committees and sponsor permission to activate sites is received. Any additional terms set by the competent authorities and ethics committees shall be followed. Sites will be individually activated by the Chief Investigator and team; this will not occur until site approval is granted.

The trial team will take day-to-day responsibility for ensuring compliance with the requirements of Good Clinical Practice (GCP) in terms of quality control and quality assurance of the data collected as well as safety reporting. The OSIRIS Trial Management Group will communicate closely with individual sites and the Sponsor's representatives to ensure these processes are effective. The Sponsor will conduct a study risk assessment in collaboration with the Chief Investigator. Based on the risk assessment, an appropriate study monitoring, and auditing plan will be produced according to Sponsor Standard Operating Procedures. Any changes to the monitoring plan must be agreed by the Sponsor and Chief Investigator. The Chief Investigator will ensure that the protocol and study is conducted in compliance with the principles outlined in the ISO14155 GCP guidelines and subsequent amendments, current UK Policy Framework for Social and health care research (2017), the World Medical Association Declaration of Helsinki, the Sponsor's and trial specific Standard Operating Procedures, and other regulatory requirements. The study will not commence until Sponsor permission to activate sites is received. Sites will be individually activated by the Chief Investigator and team; this will not occur until site approval is granted.

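### Blocks of 2 and 4 are disclosed and hospitals are randomised one request at a time, so the next allocation is predictable well above chance, and the protocol does not fix the hospital order first

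*Protocol*

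**What the plan says.** Section 12.2 sets the unit and ratio: "Clusters (hospitals) will be randomised to either intervention or control with a 1:1 allocation ratio". It gives the block sizes, "Random permuted blocks randomisation with block sizes of m=4 and 2 will be used", and adds: "This is a restricted randomisation scheme without stratification". All hospitals therefore come from a single list. The section does not say how the two sizes are mixed.

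Section 12.3 describes the process. The trial statistician writes the code, an independent statistician in the trials unit (PCTU) generates the live list, and the unit carries out the randomisation remotely. "A member of the research team who is un-blinded will be authorised to request randomisation of a cluster via email". The request goes to the independent statistician, "who will return the allocation also via email within one working day". The section then defers detail: "Further details will be explained the Data Management plan". That plan is not at hand.

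Neither section says that the order of hospitals is fixed before requests are made, that hospitals are allocated in groups, or that the requester is kept from the block sizes or from earlier results.

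**The concern.** Two and four are the smallest block sizes possible at 1:1. With one list, single requests and a reply after each, the requester can keep a running tally. Concealment of the next allocation then rests on the requester not using that tally.

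This matters more here than in an individually randomised trial. The hospital is the only level at which anything is randomised (section 17.3), there are 40 of them (section 8.1), and the trial is open (section 7.1). If the next allocation can be guessed and the next hospital can be chosen, a willing or well-organised hospital can be put forward when the intervention is due. The primary models (section 17.4) adjust for age, procedure, Charlson score and, for the SF-12 Mental Component Summary (MCS), its baseline value. They contain no hospital-level covariate. The random intercept describes variation between hospitals; it does not correct for which hospitals ended up in which arm.

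**Working it through.** The protocol gives no figure for predictability, so there is none to reproduce.

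**Inputs.** 40 hospitals (8.1); 1:1 allocation, block sizes 2 and 4, one list (12.2); the requester sees each result (12.3). *Assumption:* the sizes are drawn at random with equal probability. *Guessing rule:* name the arm that is behind; toss a coin when the arms are level.

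**Correct guesses.**
- Block of 2: the first allocation is a coin toss (0.5) and the second is always guessed correctly (1). Total 1.5 of 2, or 75%.
- Block of 4: first 0.5; second 2/3; third (2/3 × 0.5) + (1/3 × 1) = 2/3; fourth 1. Total 2.83 of 4, or 70.8%.
- Equal mix: (1.5 + 2.83) / (2 + 4) = 72.2% in the long run. A simulation of 20,000 lists of 40 gives 72.0%, about 29 of 40 hospitals against 20 by chance.

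The best possible guess, made with knowledge of the block sizes, has the same hit rate as this simple rule. The 72% therefore needs only the past allocations. Knowing the sizes adds certainty about some of them.

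**Where the guess is informative.** It beats a coin toss when the arms are unequal: 1 allocation in a block of 2, and 1 + 1/3 + 1 = 2.33 in a block of 4. (1 + 2.33) / 6 = 55.6% in the long run; the simulation gives 55%. About 45% of allocations remain a coin toss.

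**Allocations that are certain.** An imbalance of 2 can arise only in a block of 4 whose first two allocations agree (probability 1/3). Both remaining allocations are then known. Per 6 allocations (one block of each size): 2 × 1/3 = 0.67, and 0.67 / 6 = 11.1% in the long run. The simulation gives 10.7%, and 0.107 × 40 is about 4 hospitals.

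**Sensitivity to the assumed mix.**

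| Scheme | Correct | Certain |
|---|---|---|
| One third blocks of 2 | 71.4% | 13.0% |
| Equal mix | 72.0% | 10.7% |
| Two thirds blocks of 2 | 72.8% | 8.0% |
| Alternating 4 and 2, order known | 72.2% | 38.9% |

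**Would larger blocks help?** With sizes known to the guesser, mixed blocks of 4 and 6 give 68.9% correct and 5.6% certain; mixed 4, 6 and 8 give 67.7% and 2.4%. The certain allocations become rarer, but the hit rate hardly moves. If a self-contained batch (for example 8 hospitals, 4:4) is allocated together, prediction within it falls to 50%.

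**Possible effect on the outcomes.** With the protocol's intra-cluster correlation of 0.01 (17.1), the between-hospital standard deviation is √0.01 × 16 = 1.6 points on the Decision Regret Scale (DRS) and √0.01 × 11 = 1.1 points on the MCS. Take an extreme assumption: the requester knows every hospital's true level, picks freely from all 40, and uses the best or worst hospital left whenever the guess is informative. Simulated bias is then about 1.6 DRS points (target difference 7.5) and 1.1 MCS points (margin 3.5). For scale, with 600 × 0.8 = 480 analysed and a design effect of 1 + 11 × 0.01 = 1.11, the standard error is SD × √(4 × 1.11 / 480), or 1.5 and 1.1 points. The extreme bias is thus about one standard error on each outcome.

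**The case against.** The strongest reply is that steering is nowhere described. A reader might infer from section 21 ("Sites will be individually activated by the Chief Investigator and team") that the team which activates sites also decides which hospital is randomised next. The text does not support that. The sentence concerns activation once site approval is granted; it does not mention randomisation, and nothing says that activation order is allocation order. Section 12.3 authorises one un-blinded member to make requests and does not say who sets their order. This part of the objection stands in full.

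A reader might also infer that most allocations are known in advance. They are not: about 45% are coin tosses, about 11% are certain, and the rest are better-than-chance guesses.

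The process also has real safeguards. An independent statistician generates the live list, the unit randomises remotely, and the Data Management plan may fix the order or use batches. The independent list-holder prevents the list being read. It does not prevent inference from allocations already returned. The plan cannot be checked, but a safeguard that protects the only randomised level belongs in the section that describes the procedure.

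On harm, even the extreme scenario gives a bias well short of the DRS target and the MCS margin, and it needs knowledge and freedom that the protocol does not show. Adjusting for baseline MCS may remove part of any MCS bias. Both points stand. The bound does not, however, cover a larger treatment effect at keen hospitals. Small blocks also keep the arms balanced if fewer than 40 hospitals join, which is a legitimate reason for choosing them.

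**Conclusion.** The concern holds as a weakness in a stated procedure. It is not evidence that allocation has been or will be manipulated. With the disclosed block sizes, one list, and single requests by someone who sees each reply, the next hospital's allocation can be guessed correctly about 72% of the time against 50%, and about 11% of allocations are certain. These figures assume a random equal mix of the two sizes. The hit rate is stable across plausible mixes; the certain share would rise to about 39% if the sizes alternated in a known order. The protocol leaves the order of hospitals open, so it does not prevent a correct guess from being used, and the models have no hospital-level covariate to absorb the result. The remedy is cheap enough to justify the change.

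**What to change.** Add to section 12.3 at least one of the following:

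- The order of hospitals is logged with the PCTU before any allocation is released.
- Hospitals are allocated in self-contained batches, for example 8 at a time, 4:4.
- Requests come from someone with no access to earlier allocations.

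The first two stop a correct guess from being used to choose the next hospital; the third removes the information on which the guess rests.

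In addition, take the block sizes out of section 12.2 and leave them with the independent statistician. As the present sizes are already disclosed, this has an effect only if the list for hospitals not yet randomised is redrawn with different sizes. Neither withholding the sizes nor enlarging the blocks is enough alone: the hit rate does not depend on knowing the sizes, and it stays near 68% with mixed blocks of 4, 6 and 8.

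The cost is a few sentences of protocol text and either a small administrative step or a short wait to fill a batch. Logging the order needs no new list; batches or new block sizes need one for the remaining hospitals. Sample size and analysis are unchanged.

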## 12.3 Randomisation procedure

The code creating the randomisation list will be prepared by the trial statistician. The live allocation list will be generated by an independent statistician from within the Pragmatic Clinical Trials Unit (PCTU). Manual randomisation will be carried out remotely by the PCTU. A member of the research team who is un-blinded will be authorised to request randomisation of a cluster via email to the named independent statistician who will return the allocation also via email within one working day. PCTU will designate a standby who can provide allocations should the independent statistician be unavailable. Further details will be explained the Data Management plan which will be agreed and signed off between the trial study team and PCTU.

# 12.4 Study assessments

#### Screening

Checklist to ensure the patient meets the eligibility criteria

#### Demographic information

- Date of informed consent
- Initials
- Age
- Sex
- Full Name and Date of Birth for registry linkage
- Residential postcode for registry linkage
- NHS number for registry linkage
- Ethnic background
- Trial ID (generated automatically at the point of registration)

#### Baseline data

BMI category

- Laboratory data (preoperative haemoglobin, estimated glomerular filtration rate)
- Co-morbid disease including mental illness
- Quality of life according to EQ-5D-5L
- 12-Item Short Form Survey

## Index decision making episode

- Use of the decision aid intervention
- Details of planned and actual treatment

## Post-clinic follow up

- SDM-Q-9
- Healthcare use questionnaire
- Predicted post-operative quality of life according to EQ-5D-5L

## Surgical admission

- Date of surgery (Patients who do not undergo surgery will be coded as 'not applicable').
- Date of discharge
- Patient vital status (dead/alive, cause of death)
- Discharge destination

## Follow-up data

## 30-day after date of surgery follow-up

- Patient vital status (dead/alive)
- Complications measured according to Clavien-Dindo scale (Patients who don't undergo surgery will be coded as 'not applicable'.)
- Patients discharge location
- Quality of life according to EQ-5D-5L

## 180-days after index decision making episode follow-up

- Patient vital status (dead/alive)
- Hospital admissions
- Quality of life according to EQ-5D-5L

OSIRIS Protocol v2.0 20.11.2023 Page **20** of **46** 

- 12-Item Short Form Survey
- Healthcare use questionnaire
- Decision regret score

## Supplementary forms

- Withdrawal
- Protocol deviation
- Safety report

## 12.5 Training and preparation

The training packages for the intervention have been developed and tested in previous projects within the OSIRIS programme. The materials will provide easily understood information about the intervention and its use for both doctors and patients. Local clinical teams at the participating hospitals will receive additional training to support use of the intervention. We anticipate delivering interactive training for doctors that focuses on practical issues, combining didactic sessions, workshops and role-play followed by structured debriefing to establish clear plans for intervention use in patient encounters. We will deliver investigator training sessions and local small group training, either in person or online to standardise the delivery of the intervention.

#### 12.6 Intervention

This is a complex intervention, combining training to promote effective shared decision making for high-risk surgical patients (see above) together with a software-based decision support intervention. This software utilises a series of computational models developed by the OSIRIS team, which incorporates modelling of patient outcomes using NHS registry data, and patient-level information on quality of life outcomes after major surgery. Patients and doctors will use the intervention during all decision making encounters with the surgeons and other healthcare staff (e.g. anaesthetists, specialist nurses). By combining data sources from previous studies within this programme of work with NHS registry data the intervention will generate a forecast of important long-term outcomes for the patient. This forecast is presented using a clear and simple user interface with icon arrays and other patient friendly display methods to ensure it is correctly understood. Patients will be able to select and focus on outcomes of most relevance to them, whilst the intervention could highlight important outcomes which the patient might not have considered.

#### 12.7 Control

In control group hospitals, shared decision making for high-risk patients will follow current local practices. There will be no additional training or changes to care processes for these sites.

## 12.8 Mixed method process evaluation of the OSIRIS cluster trial

The process evaluation will examine how the intervention works in practice during the trial, focusing on the national-level context for introducing shared decision making (macro-level), the organisational challenges of implementing a new service model based on the intervention (meso-level), and the fine-grained detail of how the intervention shapes shared decision making (micro-level).

#### Setting and data collection

At macro-level, we will conduct up to **ten interviews** with a maximum variation sample of national stakeholders (ensuring representation from Royal Colleges, policymakers and patient groups), combined with analysis of up to ten documents (identified e.g. via Kings Fund library) to understand how national initiatives/guidance supports or inhibits shared decision making.

At the meso-level, we will conduct 12 episodes of observation in six clinics in intervention sites to understand how the intervention is adapted and delivered. The focus will be on observing the work involved in delivering the intervention, involving physically visiting selected clinics and observing the clinical/administrative work that takes place as staff seek to integrate the intervention with the existing routines of the clinic. Naturalistic interviews with clinicians and (where relevant) administrators during observation visits will enable 'on the job' discussion about what they are doing and why they are doing it (since people often find it easier to talk about the detail of their work while they are actually doing it), of how well they felt the training and implementation package prepared and supported them, and how challenges in using the intervention are identified, negotiated and (where relevant) resolved. Data will be recorded in field notes and supplemented with contextual data for each site (e.g. hospital size, surgical procedure volume).

At micro level, in the same six clinics, we plan evaluation of selected consultations (to examine intervention use in vivo) and matched patient/clinician interviews (to explore how they understand and respond to the intervention, how local/organisational context shapes intervention use and any unintended consequences). We will audio-record (with consent) up to **24 decision making consultations** with a purposive sample of **between 12 and 18 doctors**, (ensuring a mix of clinical experience and hospital type/location). We will conduct interviews (face-to-face or telephone) with the same doctors and patient **24 patients** (ensuring a mix of clinical condition, age, gender, ethnicity and social circumstances) about their perceptions of the intervention. Doctor and patient interviews will be audio-recorded with consent.

